At the initial visit, patients randomized to the E group were advised to download the Euglyca application on their smartphones and they were asked to use the application for the calculation of the bolus insulin dose. Patients randomized to the C group were advised to calculate bolus insulin dose, the way they used to do. Patients repeated their visit to the endocrine pediatric clinic at 3, 6 and 12 months, the latter set as the terminal time-point of this study following the initial visit. At all 4 visits, anthropometrics (weight, height, BMI), blood pressure measurement and heart rate were noted down, while a peripheral blood sample was drawn from all patients in the morning of each visit after an overnight fast for measurement of glycemia and glycosylated hemoglobin (HbA1c) levels. Glucose measurements between 70 and 180 mg/dl were categorized as normoglycemia; any glucose measurement below 70mg/dl was categorized as hypoglycemia; glucose measurements at two hours postprandial measurement found above 180mg/dl were categorized as hyperglycemia. At baseline (first visit), at 6 months (third visit) and at terminal time-point (12 months) all patients filled the World Health Organization-Standard DTSQ. Patients' logbooks and readings from their glucose meters were reviewed by the physicians and nutritionist of the department at each of the four visits and the percentage of normoglycemic, hypoglycemic and hyperglycemic episodes during the preceding trimester was calculated for each patient.

The change of HbA1c values from baseline to the terminal time-point for each group was set as primary outcome, while the percentage of normoglycemic, hypoglycemic and hyperglycemic events over the total number of glucose measurements during the preceding trimester of each visit was set as secondary outcome.

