## Statistics

Sample size was determined by estimating the change in HbA1c values (primary outcome) based on previous studies (7, 8), assuming 0.5% reduction in HbA1c in the intervention group with 80% power and 5% significance level. Power calculation resulted in 14 patients per group, while the target of the study had been set at recruitment of 80 patients altogether. Results are reported as mean  $\pm$  standard deviation (SD) for quantitative variables. The absolute difference in a quantitative variable between two different time points was defined as  $\Delta$ . All quantitative variables (HbA1c;  $\Delta$ HbA1c; percentages of normoglycemic, hypoglycemic and hyperglycemic events over a total number of glucose measurements; DTSQ's scores) were normally distributed and they were compared between the two studied groups of patients at the different time-points by employing General Linear Models ANOVA and Bonferroni post-hoc test. Repeated measures ANOVA involved one factor between patients (factor "Group" with two levels) and one factor for the repeated measures within patients (factor "time" with 4 or 3 levels depending on the compared variable). Qualitative variables (gender and type of therapy) were compared by employing  $\chi^2$  (chi square) test after having computed absolute and relative frequencies (percentages %), Statistical significance was set at  $P<0,05$ . An intention to treat analysis was followed. IBM SPSS V23 Chicago, USA software was used for the statistical analysis.

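### Does wording the primary outcome as HbA1c change per group leave a within-group fall open as the trial's primary result?

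*Combined protocol and SAP*

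**What the plan says.** The Protocol section sets the outcome: "The change of HbA1c values from baseline to the terminal time-point for each group was set as primary outcome". It places the follow-up visits "at 3, 6 and 12 months, the latter set as the terminal time-point of this study", so the interval is 0 to 12 months.

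The Statistics section defines Δ as the difference between any two time points. It names ΔHbA1c among the quantitative variables that were "compared between the two studied groups of patients at the different time-points by employing General Linear Models ANOVA and Bonferroni post-hoc test". It also describes a repeated-measures ANOVA with a two-level Group factor and "one factor for the repeated measures within patients", which has four levels for HbA1c.

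The sample size rests on "assuming 0.5% reduction in HbA1c in the intervention group with 80% power and 5% significance level", and "Power calculation resulted in 14 patients per group". The recruitment target was 80 patients, 40 per group under equal allocation.

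**The concern.** Three features invite a within-group reading. The outcome is stated per group. The 0.5% effect is stated for the intervention group, not as a difference from control. No sentence names the between-group difference in 0–12 month change, or the group-by-time term, as the test that decides the trial.

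The stake is real in principle. Both arms attend the same visits, and logbooks and "readings from their glucose meters were reviewed by the physicians and nutritionist of the department at each of the four visits". That attention could lower HbA1c in both arms without any app effect. A before–after test in the app group would count such a fall as benefit, and so would a claim that the app group changed significantly while control did not. The between-group difference removes a shared fall and is the contrast that randomization protects.

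**Working it through.** **1. Does the sample size reveal which test was meant?** From the Statistics section: effect 0.5, power 80%, significance 5%, result 14 per group. Neither the SD nor the sidedness is given, so the figure cannot be reproduced directly. Taking the test as two-sided and solving for the SD, with (1.960 + 0.842)² = 7.849:

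- Two-sample: n per group = 2 × SD² × 7.849 / 0.5². At SD 0.47 this is 2 × 0.2209 × 7.849 / 0.25 = 13.9, so 14.
- Paired, within one group: n = SD² × 7.849 / 0.5². At SD 0.667 this is 0.4449 × 7.849 / 0.25 = 14.0.

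With the t distribution the SDs are about 0.45 and 0.62. The stated 14 fits either design at an unremarkable SD, so it does not settle the question.

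**2. What would a within-group primary test cost?** Assumptions, none from the documents: no app effect, both arms truly fall by the same amount f, SD of change s. With 40 per group, the chance of a significant fall in the app group is the upper tail of a noncentral t with 39 df, noncentrality f × √40 / s and critical value 2.023. At s = 0.8 and f = 0.2 the noncentrality is 0.2 × 6.325 / 0.8 = 1.58.

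| SD of change | f = 0.2 | f = 0.3 |
|---|---|---|
| 0.6 | 0.538 | 0.869 |
| 0.8 | 0.338 | 0.638 |
| 1.0 | 0.234 | 0.456 |

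The chance p(1 − p) that the app group is significant and control is not, at SD 0.8, is 0.338 × 0.662 = 0.224 for f = 0.2 and 0.638 × 0.362 = 0.231 for f = 0.3. The between-group test wrongly favours the app with probability 0.025 in every cell. With f = 0 the within-group test also gives 0.025, so there is no inflation without a shared fall.

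**3. Does the plan lead to that test?** Set the sections side by side:

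- The Protocol section supplies the variable (HbA1c change) and the interval (baseline to 12 months).
- The Statistics section supplies the comparison. The only comparison of quantitative variables it puts into words is between the two groups, and ΔHbA1c is in its list.
- The Bonferroni post-hoc test is attached to that between-group sentence. If it were read as applying to the time factor, it would compare visit means pooled over both groups. A baseline-to-12-month test inside the app group would need a simple-effects step that is not described.

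The number of comparisons in such a step would also be a guess. At SD 0.8, dividing alpha by 6 (pairs of four visits) gives 0.130 for f = 0.2 and 0.355 for f = 0.3. Dividing by 28 (pairs of the eight group-by-visit cells) gives 0.051 and 0.185.

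**4. Is the between-group test workable at 40 per group?** For a difference of 0.5, with noncentrality 0.5 / (s × √(2/40)) and 78 df, power is above 0.99 at SD 0.45–0.47, 0.788 at SD 0.8 and 0.598 at SD 1.0. The within-group test would have 0.971 at SD 0.8 and 0.869 at SD 1.0. That advantage could tempt someone towards the within-group result, but it exists only for a test the plan does not state.

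**The case for a change.** The strongest case for a change is that the sentence defining the headline claim does not commit to the right contrast, and that committing would cost one sentence. Δ is open to any two visits. Four visits give six intervals, and HbA1c and ΔHbA1c are both compared at several time points, so several between-group tests exist and none is labelled primary. The effect size is worded for one arm, and the sample size is silent on the design. A determined author could quote the primary-outcome sentence and report a before–after fall.

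Most of this is accurate as description. No sentence singles out the between-group 0–12 month difference, and writing one down would be harmless. But the interval is not open for the primary outcome, because the Protocol section fixes it. The per-group phrase also reads naturally as saying where change is measured, with the Statistics section saying how the arms are compared. The remaining risk is selective reporting against the plan's own stated comparison, which is not an error in the plan. The shared fall is possible but not documented: patients had already been trained and were in follow-up at the clinic, and no HbA1c threshold for entry is listed that would select for regression to the mean.

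**Conclusion.** No change follows. The plan, followed as written, produces a between-group comparison of 0–12 month HbA1c change from a model with a Group factor. A one-line label would name a test that is already there and would alter no estimate, sample size or error rate. This is a gap in detail that a competent analyst closes in the only way the Statistics section describes.

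The false-positive rates of 23% to 87% apply only if three things hold together: a within-group result is promoted to primary, both arms share a fall of 0.2 to 0.3, and the SD of change lies between 0.6 and 1.0. The documents establish none of these. This conclusion rests on reading the Protocol and Statistics sections together. It would not hold if the Statistics section had described a within-group test for HbA1c, and it does not.

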## Statistics

Sample size was determined by estimating the change in HbA1c values (primary outcome) based on previous studies (7, 8), assuming 0.5% reduction in HbA1c in the intervention group with 80% power and 5% significance level. Power calculation resulted in 14 patients per group, while the target of the study had been set at recruitment of 80 patients altogether. Results are reported as mean  $\pm$  standard deviation (SD) for quantitative variables. The absolute difference in a quantitative variable between two different time points was defined as  $\Delta$ . All quantitative variables (HbA1c;  $\Delta$ HbA1c; percentages of normoglycemic, hypoglycemic and hyperglycemic events over a total number of glucose measurements; DTSQ's scores) were normally distributed and they were compared between the two studied groups of patients at the different time-points by employing General Linear Models ANOVA and Bonferroni post-hoc test. Repeated measures ANOVA involved one factor between patients (factor "Group" with two levels) and one factor for the repeated measures within patients (factor "time" with 4 or 3 levels depending on the compared variable). Qualitative variables (gender and type of therapy) were compared by employing  $\chi^2$  (chi square) test after having computed absolute and relative frequencies (percentages %), Statistical significance was set at  $P<0,05$ . An intention to treat analysis was followed. IBM SPSS V23 Chicago, USA software was used for the statistical analysis.

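### The repeated measures model counts the pre-app visit as an outcome level; if its Group main effect is read as the arm comparison, it shows only 75% (67% for DTSQ) of the average follow-up effect

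*Combined protocol and SAP*

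**What the plan says.** The analysis model is in the Statistics section: "Repeated measures ANOVA involved one factor between patients", namely Group with two levels, and one factor within patients, time, "with 4 or 3 levels depending on the compared variable". Neither a Group-by-time term nor a baseline covariate is mentioned.

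The preceding sentence of the same section is also relevant. It says that HbA1c, ΔHbA1c, the glucose percentages and the DTSQ scores were compared between the two groups at the different time-points, using General Linear Models ANOVA with a Bonferroni post-hoc test. Δ is defined for any quantitative variable, but the list of analysed variables includes it only for HbA1c.

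The schedule is in the Protocol section:
- Visits: "Patients repeated their visit to the endocrine pediatric clinic at 3, 6 and 12 months", after an initial visit, so four in all.
- Glucose percentages: calculated at each of the four visits for the trimester before that visit.
- DTSQ: "At baseline (first visit), at 6 months (third visit) and at terminal time-point (12 months) all patients filled the World Health Organization-Standard DTSQ".
- Start of the intervention: "At the initial visit, patients randomized to the E group were advised to download the Euglyca application on their smartphones".

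The primary outcome is the change in HbA1c from baseline to 12 months. The glucose percentages are the secondary outcome. DTSQ is analysed but is not listed as either.

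**The concern.** The first glucose percentages describe a trimester that ended before any patient had been given the app, and the first DTSQ was completed at baseline. Randomization makes the expected arm difference in these values zero. They carry useful information about each patient, but none about the app.

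In a repeated measures ANOVA the Group main effect is the arm difference averaged over all levels of time. With the initial visit among the levels, a known zero is averaged in, and the estimate itself is pulled toward zero, which is more than a loss of precision. The initial-visit value is also spent on the outcome side, when on the covariate side it would remove between-patient variation.

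At stake is the analysis of the secondary glucose outcome, which includes hypoglycemia in a trial of a bolus-dose calculator, and of treatment satisfaction. The primary outcome is largely outside this point, because ΔHbA1c is compared separately.

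**Working it through.** **Does the initial visit count as a level?** Follow-up visits are at 3, 6 and 12 months, which makes 3. Adding the initial visit makes 4, the number of visits at which the glucose percentages are calculated. DTSQ has two follow-up assessments (6 and 12 months); adding baseline makes 3. The stated 4 and 3 levels fit these variables only if the initial visit is included.

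**Size of the dilution.** The documents give no figure to reproduce here. Let the arm differences at follow-up be a, b, c, with expected difference 0 at the initial visit.
- 4 levels: (0 + a + b + c)/4 = 0.75 × (a + b + c)/3.
- 3 levels (DTSQ): (0 + a + b)/3 = 0.667 × (a + b)/2.

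Relative to the average follow-up effect, these ratios hold for any time course. Relative to the 12-month effect they do not:

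| Assumed time course | Group term as share of 12-month effect |
|---|---|
| Constant from first follow-up | 75%; DTSQ 67% |
| Linear growth | (0 + 0.25 + 0.5 + 1)/4 = 44%; DTSQ (0 + 0.5 + 1)/3 = 50% |
| Half effect at 3 months, full at 6 and 12 | (0 + 0.5 + 1 + 1)/4 = 62.5% |
| Full at 3 and 6 months, half at 12 | [(0 + 1 + 1 + 0.5)/4]/0.5 = 125% |

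**Power.** The documents give no SD, correlation or expected effect for the percentages or DTSQ, so these are assumptions: 0.5 SD at every follow-up visit, equal correlation r between visits, two-sided 5%, and 40 per arm (80 patients in two equal groups). In SD units, with k time levels including the initial visit and m = k − 1 follow-up levels, the SD of each patient's summary is:
- Group over all levels: √[(1 + (k − 1)r)/k], effect 0.5m/k (0.375 or 0.333).
- Follow-up levels only: √[(1 + (m − 1)r)/m], effect 0.5.
- Follow-up levels with the initial value as covariate: √[(1 + (m − 1)r)/m − r²], effect 0.5.

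Example, k = 4 and r = 0.5: √(2.5/4) = 0.791 with effect 0.375; √(2/3) = 0.816 with effect 0.5; √(0.667 − 0.25) = 0.645 with effect 0.5. The noncentral t distribution (noncentral F for the interaction) gives:

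| Comparison | 4 levels, r = 0.5 to 0.8 | 3 levels, r = 0.5 to 0.8 |
|---|---|---|
| Group over all levels | 55% to 44% | 44% to 35% |
| Group over follow-up only | 77% to 66% | 72% to 64% |
| Group-by-time interaction (not named) | 61% to 96% | 62% to 96% |
| Follow-up with initial value as covariate | 93% to over 99% | 88% to 99% |

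One visit compared without adjustment has 60% power at any r. With Bonferroni over 4 or 3 visits it has 38% or 42%; the plan does not state the family.

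At r = 0.3 the covariate model still leads the all-level Group term: 91% against 67% (4 levels) and 84% against 52% (3 levels).

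**The case against.** The strongest reply is that the plan never says the Group main effect is the test. It lists the factors of a design. The sentence before it compares the same variables between groups at the different time-points, and a comparison at 3, 6 or 12 months contains no pre-app value. Group has two levels, so a Bonferroni post-hoc on its main effect would have nothing to adjust, which suggests that visit-specific contrasts were intended. This stands. A reader might infer that Group is the only between-arm comparison for the percentages and DTSQ, and the text does not support that.

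A reader might also infer that a real difference would probably be missed, or that an excess of hypoglycemia would be hidden. Neither is established. The power figures rest on an assumed effect and correlation, and at r = 0.5 with 4 levels the diluted test still detects more often than not. Means with SD and comparisons at the time-points are also planned, so a follow-up excess would not be visible only through an averaged term.

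Two further replies carry less weight. First, an SD of at most 0.472, back-solved from 14 per group and a 0.5% HbA1c reduction, keeps power above 97%. That is an HbA1c value and says nothing about the percentages or DTSQ. Second, an average over follow-up is itself not the 12-month effect: under linear growth it is (0.25 + 0.5 + 1)/3 = 58% of it, and (0.5 + 1)/2 = 75% for DTSQ. This is correct, and it is why the fix also asks for the difference at each visit.

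**Conclusion.** The point holds conditionally. The pre-app visit is an outcome level for the glucose percentages and DTSQ, and the plan does not say which term or contrast of the model compares the arms. If the Group main effect is used, its estimate is 75% of the average follow-up effect, or 67% for DTSQ. Those ratios need only randomization, not a constant effect. The time-point comparisons and the ΔHbA1c comparison escape the dilution, but none is written with a baseline covariate.

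The power ranking rests on the assumed 0.5 SD, 40 per arm and equal correlation. Under those assumptions the covariate model beats the all-level Group term, the unadjusted single visit and the interaction test, although its lead over the interaction is small at r = 0.8. The case for changing the plan is a better use of data already collected. It does not depend on showing that the diluted term was the intended test.

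**What to change.** For the glucose percentages and DTSQ, restate the model in the Statistics section as follows:
- Time levels are follow-up visits only: 3, 6 and 12 months, or 6 and 12 months for DTSQ.
- The initial-visit value of the same variable enters as a covariate.
- The baseline-adjusted Group effect over follow-up is reported as the arm comparison, together with the baseline-adjusted difference at each visit, including 12 months, because the two differ if the effect changes over time.
- The family over which Bonferroni is applied is stated.

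The cost is a few sentences and a changed model statement. No new data, visits or patients are needed.

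### Intention to treat is claimed without a missing-value rule, while the named analyses keep only patients with complete values; the effect depends on whether any visit was missed

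*Combined protocol and SAP*

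**What the plan says.** All references are to the combined protocol and SAP.

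- **Analysis set (Statistics).** One sentence: "An intention to treat analysis was followed". No definition of the set follows.
- **Longitudinal test (Statistics).** "Repeated measures ANOVA involved one factor between patients" (group, two levels) and a within-patient time factor "with 4 or 3 levels depending on the compared variable".
- **Other comparisons (Statistics).** The quantitative variables, ΔHbA1c among them, were "compared between the two studied groups of patients at the different time-points by employing General Linear Models ANOVA" with a Bonferroni post-hoc test. For Δ: "The absolute difference in a quantitative variable between two different time points was defined as" Δ.
- **Software (Statistics).** "IBM SPSS V23 Chicago, USA software was used for the statistical analysis".
- **Primary outcome and visits (Protocol).** The primary outcome is HbA1c change from baseline to 12 months. Visits are at baseline, 3, 6 and 12 months; DTSQ is completed at baseline, 6 and 12 months.
- **Completeness (Protocol).** The only text that bears on it is descriptive: "a peripheral blood sample was drawn from all patients in the morning of each visit", with similar wording for the DTSQ.

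Neither section mentions a missed visit, dropout, imputation, a likelihood-based model or a sensitivity analysis.

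**The concern.** Intention to treat commits the trial to analysing every randomised patient in the allocated arm. The methods named cannot do that once a value is absent. Repeated measures ANOVA through the SPSS general linear model needs a value at every time level, so one missed visit removes the patient and discards that patient's other visits. This is a property of the procedure; the plan does not state it. A ΔHbA1c comparison cannot be computed for a patient with no 12-month value. In either case the result would be a complete-case analysis labelled intention to treat.

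Follow-up lasts 12 months in children and adolescents, and the intervention is an app that they use themselves, so non-attendance is a foreseeable event. The main stake is bias. If patients who are doing badly leave one arm, the completers in that arm look better than the arm really was, and a larger sample does not correct that.

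**Working it through.** **Inputs from the documents.** 80 randomised in two equal groups (40 each); target difference 0.5 HbA1c points; 80% power; 5% significance; three follow-up visits (two for DTSQ). The documents give no SD, no correlation between visits and no dropout rate, so everything that depends on these is an assumption.

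**The plan's own figure.** "Power calculation resulted in 14 patients per group" cannot be reproduced directly without an SD. Solved backwards with a two-sided normal approximation: SD = 0.5 / [(1.960 + 0.842) × √(2/14)] = 0.472. Sidedness and design are not stated; other readings give roughly 0.44 to 0.71. I use 0.47 as the low value and 0.79 as the high value, the latter being the SD at which 40 per group has about 80% power.

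**Patients lost, of 80, with a share p missing per follow-up visit (assumed 2 / 5 / 10%).**
- Primary ΔHbA1c: 80p = 1.6 / 4 / 8. Only a missing 12-month value counts.
- Four-visit repeated measures test: from 80p = 1.6 / 4 / 8 (the same patients miss every later visit) to 80 × [1 − (1 − p)³] = 4.7 / 11.4 / 21.7 (independent misses).
- Three-visit DTSQ test: from 1.6 / 4 / 8 to 80 × [1 − (1 − p)²] = 3.2 / 7.8 / 15.2.

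**Power for a difference of 0.5 (two-sided t test) at 40 / 38 / 36 per group.** SD 0.47: 99.7 / 99.6 / 99.4%. SD 0.79: 79.8 / 77.7 / 75.4%.

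**Bias in the completers' ΔHbA1c difference.** Suppose the fraction p of one arm with the worst 6-month change do not return, and nobody leaves the other arm. Then

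bias = SD × c × φ(z)/(1 − p),

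where z is the upper-p normal quantile and c is the correlation between the 6- and 12-month changes. With an assumed 3-month correlation r that decays geometrically with time, c = 0.5 × √(1 + r²), which is 0.625 / 0.656 / 0.679 for r = 0.75 / 0.85 / 0.92.
- p = 10%: φ(z)/(1 − p) = 0.1755/0.90 = 0.195. SD 0.47: 0.195 × 0.47 × (0.625 to 0.679) = 0.057 to 0.062. SD 0.79: 0.096 to 0.105.
- p = 5%: 0.1031/0.95 = 0.1086. SD 0.47: 0.032 to 0.035. SD 0.79: 0.054 to 0.058.
- Graded selection (10% missing in one arm, assumed odds ratio 2 per SD of 6-month change, by simulation): 0.02 to 0.04.

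For scale, the standard error of the difference at 40 per group is SD × √(2/40) = 0.105 (SD 0.47) to 0.177 (SD 0.79).

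**What a model using earlier visits recovers.** In simulation (1,000,000 patients per setting), regression on baseline, 3 and 6 months leaves at most about 0.002 of the 6-month-driven bias. That follows from the set-up, because dropout there depends only on observed values. If the 10% who leave are instead the poorest responders at 12 months, the completers are off by SD × 0.195 = 0.09 (SD 0.47) to 0.15 (SD 0.79), and 58-59% of that remains in the model.

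**Cost of baseline adjustment with complete data.** For a baseline-to-12-month correlation ρ, the adjusted estimate differs from the change-score estimate with SD (1 − ρ) × SD_Y × √(2/40), where SD_Y = SD/√(2(1 − ρ)). For ρ = 0.5 / 0.7 / 0.85 this is 0.053 / 0.041 / 0.029 (SD 0.47) and 0.088 / 0.068 / 0.048 (SD 0.79). The standard-error ratio is √((1 + ρ)/2) = 0.866 / 0.922 / 0.962, a reduction of 13% to 4%.

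**The case against.** The strongest reply is that the documents describe complete data. Blood is reported as drawn from all patients at each visit, the DTSQ as completed by all, and event percentages as calculated for each patient. Statistics is written in the past tense. Read literally, all 80 patients enter every analysis and the point has no numerical effect. This stands as a limit on the concern. It does not close the gap, because these sentences describe visit procedure; they neither report completeness nor give a rule for a missing value.

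Three further replies also stand in part.
- The loss from the repeated measures test does not reach the primary comparison. A reader might infer that up to 21.7 of 80 patients could drop out of the primary result. That figure belongs only to the four-visit test under independent misses at 10%.
- The bias of 0.06-0.10 needs exactly the worst 10% of one arm to leave and nobody from the other. At 5%, or with graded selection, it is smaller, and in every 6-month scenario it is below the standard error.
- Replacing the model also brings in baseline adjustment, which is a choice separate from missingness. If results are known, the change could look post hoc. That is a reason to label it and to show the unadjusted comparison beside it.

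A reader might also infer that patients were in fact lost and that the intention-to-treat statement is false. The documents report no missed visit and do not support that.

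**Conclusion.** The concern holds as a conditional one and should be fixed. The plan claims intention to treat, names methods that keep only patients with the needed values, and gives no rule for a missed visit or a missing 12-month HbA1c. With complete data there is no effect.

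If values are missing, the likely harm to the primary result is moderate: about 6% to 20% of the 0.5-point target effect under the 6-month dropout scenarios (0.03/0.5 to 0.10/0.5). The effect on power depends on the unknown SD: negligible at 0.47, and about 4 percentage points at 0.79 if each arm falls to 36.

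It would be too strong to say that a mixed model removes the bias. It does so only if missingness depends on observed values (missing at random); more than half remains if dropout follows the unseen 12-month value. All sizes rest on assumed SDs, correlations and dropout patterns.

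**What to change.** In Statistics:
- Replace repeated measures ANOVA for HbA1c with a linear mixed model (SPSS MIXED) on all available 3-, 6- and 12-month values, with group, categorical visit, group × visit, baseline HbA1c as covariate and unstructured covariance.
- Name the 12-month group contrast with its 95% CI as the single primary result, and report the unadjusted ΔHbA1c comparison alongside.
- Define the intention-to-treat set as all 80 randomised patients as allocated, and report completeness by arm and visit. Include a count of patients with no post-baseline HbA1c, who add nothing to the model contrast.
- Only if 12-month HbA1c values are missing, add one sensitivity analysis under a not-missing-at-random assumption that covers all such patients. Multiple imputation within the primary analysis is not needed.

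Cost: revised wording and some analysis time; no new data or visits, and the model runs in the software already named. Even with complete data the adjusted estimate can differ by chance from the change-score estimate, typically by 0.03-0.09, in exchange for a standard error about 4-13% smaller (assumed correlation 0.85 to 0.5). If results have already been seen, label the change as post hoc. If no value is missing, one sentence saying so settles the missing-data question.
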